# 1.1 Protocol Amendment: Summary of Changes

#### **Previous Protocol Versions**

[figure not shown]
Protocol	Date
Original	17 May 2017
Amendment 1	29 June 2017
Amendment 2	24 May 2018
Administrative Change 1	09 May 2019
Administrative Change 2	13 May 2020
Amendment 3	05 September 2019
Amendment 4	16 November 2020
Amendment 5	08 October 2021

# The purpose of this amendment is to:

 Update Section 5.3.1.1, Study Procedures, Endometrial Biopsy and Appendix C, Study Activities.

Rationale: Based on FDA correspondence to elagolix-AB IND 115528 (April 21, 2022, FDA Advice/Information Request, Reference ID: 4971727), the endometrial biopsy at Month 36 was reinstated and the criteria revised so that the endometrial biopsy is required regardless of endometrial thickness.

• Correct administrative and typographical errors throughout the document.

#### 1.2 Synopsis

AbbVie Inc.	Protocol Number: M16-283
Name of Study Drug: Elagolix (ABT-620)	Phase of Development: 3b
Name of Active Ingredient: Elagolix sodium	Date of Protocol Synopsis: 02 May 2022

**Protocol Title:** A Phase 3b Study to Evaluate the Long-Term Safety of Elagolix in Combination with Estradiol/Norethindrone Acetate for the Management of Heavy Menstrual Bleeding Associated with Uterine Fibroids in Premenopausal Women

#### **Objectives:**

The objectives of this study are 1) to assess the safety of elagolix 300 mg BID in combination with E2/NETA (estradiol 1.0 mg/norethindrone acetate 0.5 mg QD) compared to placebo at 12-months in premenopausal woman with heavy menstrual bleeding associated with uterine fibroids, 2) to characterize the impact of elagolix 300 mg BID with E2/NETA on bone mineral density (BMD) in women with heavy menstrual bleeding associated with uterine fibroids after up to 48-months of treatment.

**Investigators:** Multicenter

**Study Sites:** Approximately 175 sites

**Study Population:** Premenopausal female subjects (aged 18 to 50 years, inclusive) with uterine fibroids and HMB (> 80 mL blood loss per menstrual cycle).

Number of Subjects to be Enrolled: Approximately 500

#### Methodology:

This Phase 3b, sequential, randomized, 12-month double-blind placebo-controlled, 36-month open-label, multi-center study is designed to evaluate the long term safety of elagolix with add back therapy in women with HMB associated with uterine fibroids. Approximately 500 subjects will be randomized in a 2:1 ratio to one of the following two treatment groups:

- 1. Elagolix 300 mg BID plus E2/NETA (estradiol 1.0 mg/norethindrone acetate 0.5 mg QD) (n = 335) for 48-months
- 2. Placebo (n = 165) for 12-months, followed by elagolix 300 mg BID plus E2/NETA (estradiol 1.0 mg/norethindrone acetate 0.5 mg QD) for 36-months

[figure not shown]
Subjects randomized to elagolix 300 mg BID plus E2/NETA in the 12-month Treatment Period will receive the same treatment during the open label Treatment Period. Subject randomized to placebo in the 12-month Treatment Period will switch to elagolix 300 mg BID plus E2/NETA during the open label Treatment Period after completing the 12-month Treatment Period.

#### **Study Duration:**

The total duration for this study is up to 77 months.

The study consists of 4 periods:

- Washout Period up to 10 months prior to Screening (only applicable if subject is taking exclusionary medication at the time of consent; duration of washout depends on the type of exclusionary medication being taken).
- Screening Period approximately 2.5 to 5 Months prior to first dose of study drug.
- Treatment Period up to 48-month treatment duration.

#### **Study Duration (Continued):**

• Post-Treatment Follow-Up Period – up to 12-month duration following the last dose of the study drug. Subjects are expected to enter Post-Treatment Follow-Up after completing Treatment Month 48, or at any time a subject prematurely discontinues during the Treatment Period.

#### **Washout Period:**

Following informed consent, subjects, who have been taking exclusionary medications, must enter a Washout Period. Subjects must complete the Washout Period and then have at least 1 menses (refer to Table 2) after completion of washout, prior to entering the Screening Period. The duration of washout period is based on the excluded medication as described in the protocol. The following study procedures may be performed: medical, social and gynecological history, a physical examination with vital signs, urine pregnancy testing; protocol-related adverse event review and documentation of current medications and a pelvic ultrasound (transabdominal [TAU] and transvaginal [TVU]) may be performed after obtaining informed consent and prior to a subject entering the Washout Period in order to establish the presence of a qualifying fibroid(s) or uterine volume to avoid an unnecessary and lengthy washout period. Subjects will also begin the use of dual non-hormonal contraception and receive counseling on the importance of consistent, appropriate and effective use of birth control and will have contraceptives dispensed as necessary.

#### **Screening Period:**

[figure not shown]
Following informed consent (if Washout was not required), subjects will enter into the approximately 2.5 to 5 Months Screening Period to establish eligibility based on inclusion and exclusion criteria, including the following assessments: a pelvic ultrasound (TAU and TVU); a saline infusion sonohysterography (SIS); an endometrial biopsy; a Pap test; a mammogram in subjects 39 years of age or older (at the time of randomization) if one was not performed within 3 months prior to Screening; a dual energy x-ray absorptiometry (DXA) scan (for BMD). During the Screening Period, subjects must demonstrate MBL of > 80 mL for each of two menses as measured by the Alkaline Hematin method which quantifies the amount of blood loss on sanitary products. Subjects will be dispensed sanitary product collection kits for 2 to 3 menstrual cycles and will be required to collect all sanitary products (with or without visible blood) on days with menstrual bleeding or spotting, and must return the products to the site within approximately 5 days after cessation of menses. Subjects are required to use dual non-hormonal contraception (as applicable), contraceptive counseling will be provided and contraceptives dispensed, as necessary.

#### Year 1 Treatment Period:

The Treatment Period begins with Day 1, which will occur between cycle Days 1 to 10 of the first day of menses (defined as full menstrual flow), for all subjects who meet eligibility criteria during the Screening Period.

On Day 1 of the 12-month Treatment Period, subjects will be randomized to receive either placebo (n = 165), or elagolix 300 mg BID plus E2/NETA (n = 335). Study drug kits will be dispensed to subjects at each on-site visit. Subjects entering the 12-month Treatment Period will have on-site visits at Day 1, Months 3, 6, 9 and 12; phone visits will be made at Months 1, 2, 4, 5, 7, 8, 10 and 11.

A mammogram, pelvic ultrasound (TAU and TVU) and endometrial biopsy (based on TVU finding) will be performed in subjects at Month 12 or Premature Discontinuation Visit, if applicable; DXA scan will be performed at the Months 6, 12 and Premature Discontinuation Visit (if applicable); Vital signs assessments will be conducted at all on-site study visits, and a baseline ECG will be obtained.

#### Year 1 Treatment Period (Continued):

During Months 1 to 12, subjects will be asked to complete the following patient-reported outcome questionnaires: (UFS-QoL), Patient Global Impression of Change (PGIC based on menstrual bleeding (PGIC-MB), Site Staff will administer the and the C-SSRS – Since Last Visit questionnaire. The Investigator will complete the Physician Surgery Questionnaire (PSQ).

A urine pregnancy test will be performed at each visit throughout the Treatment Period. Home urine pregnancy test kits will be provided to subjects for use at home for the study visits when subjects are not required to come to the site. Subjects will self-administer the test and report the results to the site during the scheduled phone contact visits. A positive urine pregnancy test must be confirmed with a serum pregnancy test. If a serum pregnancy test result is positive at any time during the Treatment Period, study drug will be discontinued.

Blood samples for Clinical Safety Labs will be performed at on-site visits throughout the 12-month Treatment Period. Subjects will be counseled at each visit on appropriate and effective forms of dual non-hormonal contraceptives to promote pregnancy prevention.

Blood samples will be collected for assay of serum estradiol and to measure plasma concentrations of elagolix and norethindrone.

Adverse event and concomitant medication review will be conducted at all visits (on-site and phone visit) during the Treatment Period.

[figure not shown]

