#### Year 2, 3 4 (Open-Label) Treatment Period (Continued):

A urine pregnancy test will be performed at each visit throughout the Treatment Period. Home urine pregnancy test kits will be provided to subjects for use at home for the study visits when subjects are not required to come to the site. Subjects will self-administer the test and report the results to the site during the scheduled phone contact visits. A positive urine pregnancy test must be confirmed with a serum pregnancy test. If a serum pregnancy test result is positive at any time during the Treatment Period, study drug will be discontinued. Subjects will be counseled at each visit on appropriate and effective forms of dual non-hormonal contraceptives to promote pregnancy prevention.

Subjects will continue to provide blood samples for Clinical Safety Labs, during the on-site visits.

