## 5.2.3.3 Iron Supplementation

Excessive blood loss from heavy menses may result in iron deficiency anemia. Iron deficiency anemia is defined by the World Health Organization (WHO) as an Hgb concentration below 12~g/dL (120~g/L) for non-pregnant women. Subjects entering the study with anemia or who develop anemia during the study, if not already taking iron supplements, should be prescribed iron supplementation by the Investigator, as per standard of care. If the Investigator does not prescribe iron supplements for subjects with a Hgb < 12g/dL, the reason should be documented in source documents.

The recommended oral dose of ferrous sulfate is 300 to 325 mg following the diagnosis of anemia. During Screening, all subjects with an Hgb level < 7 g/dL will be retested after receiving iron supplements; these subjects will only be eligible to randomize if their Hgb results meet eligibility prior to Day 1 (Randomization) and has not required a blood transfusion within 60 days prior to Day 1. If a subject is unable to tolerate ferrous sulfate

then ferrous gluconate, liquid iron or intravenous (IV) iron may be prescribed. If subjects experience constipation from iron supplement use, stool softeners may be prescribed. All iron supplements taken during the study, from Screening through the final visit, must be recorded on the concomitant medications eCRF.

Further instructions on the provision of iron supplementation and stool softeners will be provided separately from this protocol.

[figure not shown]

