## **Clinical Laboratory Tests**

Samples will be obtained for the laboratory tests listed in Table 4, at the time points indicated in Appendix C, Study Activities.

Table 4. Clinical Laboratory Tests

Hematology	Clinical Chemistry (After Minimum 8-Hour Fast)	Urinalysis
Hematocrit Hemoglobin Red Blood Cell (RBC) count White Blood Cell (WBC) count Neutrophils Bands (if indicated) Lymphocytes Monocytes Basophils (if indicated) Eosinophils (if indicated) Platelet count (estimate not acceptable) Mean Cell Volume of RBC	Sodium Potassium Chloride Bicarbonate Blood Urea Nitrogen (BUN) Serum creatinine Glucose Calcium Total protein Albumin Total bilirubin Serum glutamic-pyruvic transaminase (SGPT/ALAT) Serum glutamic-oxaloacetic transaminase (SGOT/ASAT) Alkaline phosphatase Serum iron¹ Serum ferritin¹ Total iron binding capacity (TIBC)¹ Vitamin D Testing¹	Specific gravity Ketones Protein Blood Glucose pH  Lipid Panel (After Minimum 8-Hour Fast)  Low-density Lipoprotein (LDL) cholesterol High-density Lipoprotein (HDL) cholesterol Triglycerides Total cholesterol
(MCV) Mean Corpuscular Hemoglobin (MCH) Mean Corpuscular Hemoglobin Concentration (MCHC)  Pregnancy Test  Serum pregnancy (only completed if urine pregnancy test is positive)		Endocrine Panel  Follicle-stimulating hormone (FSH)  Reflexive Thyroid Stimulating Hormone (TSH)

1. To be completed at Screening visit only.

Laboratory samples indicated in Table 4 will be assessed using a certified central laboratory selected for this study and these data will be used for data analysis. The central laboratory will provide instructions regarding the collection (including any fasting requirements), processing and shipping of samples. Blood draws should be performed after vital signs and ECG recording are conducted at a visit.

Clinical chemistry samples should be obtained in the morning following an overnight fast (minimum of 8 hours); however, there may be circumstances when the sample is obtained later in the day and/or not under fasting conditions. If the sample was obtained with less

than 8 hours of fasting, the source documents and the lab requisition should be marked to indicate that the sample was obtained under non-fasting conditions.

[figure not shown]
All clinical laboratory samples will be shipped to the central laboratory, with the exception of the venous blood sample for alkaline hematin analysis which will be sent to the Alkaline Hematin Laboratory during screening.

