## Appendix C. Study Activities

		f Applicable							,	Year 1								
Procedure	WO Period	SCR Visit	Cycle 1 -3 ‡ PCV b	D 1°	M 1	M 2	M 3	M 4	M 5	M 6	M 7	M 8	M 9	M 10	M 11	M 12	Unsch Visit	PD (If Appl.)
Informed Consent	X	X&																
Phone Visit d					X	X		X	X		X	X		X	X			
Medical/Social History	X	X &		Xe														
Gynecological/ Obstetrical and Uterine Fibroid History	X	X &		X e														
Complete Physical Examination; Height (H); Weight (W)	X*	X (H, W) \$		X*,e												X (W) \$		X (W) \$
Gynecological (External Genitalia, Pelvic and Breast) Examination		X														X		X
Vital Signs	X	X	X	Xe			X			X			X			X	X	X
12-Lead Electrocardiogram (ECG)		X																
Mammogram		$X_{\infty}$														X f		X g
Pap Test		X																X g
Endometrial Biopsy h,i		X														X		X g
Pelvic Ultrasound @ : TAU, TVU	X j	X &		$X^k$												X		X g
Saline Infusion Sonohysterography (SIS) i		X																
MRI (if applicable) l		X																
DXA Scan		X								X						X		X g

[figure not shown]
		Applicab eening Per							,	Year 1								
Procedure	WO Period	SCR Visit	Cycle 1  -3 ‡ PCV b	D 1°	M 1	M 2	M 3	M 4	M 5	M 6	M 7	M 8	M 9	M 10	M 11	M 12	Unsch Visit	PD (If Appl.)
Dispense Sanitary Products and Collection Kit (Keg, Collection Bags, etc.)		X	Χ^															
Start Collection of Sanitary Products		X																
Return Sanitary Products; draw venous blood sample			X															
Clinical Safety Labs: Chemistry, Hematology, Lipid Panel and Urinalysis		X		X												X		X
Lipid Panel and Subset of Chemistry Labs: ALT, AST, Bilirubin and Alkaline Phosphatase							X			X			X					
Urine Test for Gonorrhea and Chlamydia (Optional)		X m																
Vitamin D Testing		X																
Serology (Hepatitis and HIV Screens)		X																
Endocrine: FSH and Reflexive TSH		X																
Biomarker Sample: Serum Estradiol (E2)				Xe			X n			X n			X n			X n		X n
Pharmacokinetic Sample (PK): Elagolix and NETA Plasma Concentration							X n			X n			X n			X n		X n

		Applicable							7	Year 1	Treat							

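### Appendix C schedules no hemoglobin for a continuing subject between Day 1 and Month 12 (336 days), despite the synopsis wording on safety labs and an iron rule for anemia that develops on study

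*Protocol*

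**What the plan says.** The synopsis (Section 1.2, Year 1 Treatment Period) sets on-site visits at Day 1 and Months 3, 6, 9 and 12 and then says: "Blood samples for Clinical Safety Labs will be performed at on-site visits throughout the 12-month Treatment Period". For the open-label years it says: "Subjects will continue to provide blood samples for Clinical Safety Labs, during the on-site visits".

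Section 5.3.1.1 (Clinical Laboratory Tests) hands the timing to the appendix: "Samples will be obtained for the laboratory tests listed in Table 4, at the time points indicated in Appendix C, Study Activities". Table 4 lists hemoglobin under Hematology. Its footnote to serum iron, ferritin and total iron binding capacity reads "To be completed at Screening visit only".

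The Year 1 table in Appendix C has two relevant rows:

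- "Clinical Safety Labs: Chemistry, Hematology, Lipid Panel and Urinalysis" is marked at Screening, Day 1, Month 12 and Premature Discontinuation.
- "Lipid Panel and Subset of Chemistry Labs: ALT, AST, Bilirubin and Alkaline Phosphatase" is marked at Months 3, 6 and 9.

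Section 5.2.3.3 defines anemia as hemoglobin below 12 g/dL. It covers women who are anemic at entry and those "who develop anemia during the study, if not already taking iron supplements, should be prescribed iron supplementation by the Investigator". If a woman is below 12 g/dL and iron is not prescribed, the reason has to be documented. The section gives no interval for checking hemoglobin, and ends: "Further instructions on the provision of iron supplementation and stool softeners will be provided separately from this protocol".

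**The concern.** The synopsis and the schedule do not agree. Read with Appendix C's own label, the synopsis promises hematology at every on-site visit, but the schedule gives it once a year.

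The clinical stake lies mainly in the placebo arm (about 165 women by the protocol). Entry requires more than 80 mL of blood loss in each of two screening cycles, and hemoglobin may be as low as 7 g/dL. Section 5.2.3.5 bars tranexamic acid and hormonal treatments during treatment. Under Section 5.4, heavy bleeding that needs a transfusion after 28 days of study drug leads to withdrawal. Iron is therefore the main provision left for anemia, and it depends on a hemoglobin value that is not scheduled. The women concerned are those who become anemic after Day 1 and are not on iron, and those whose known anemia worsens unobserved.

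There is a smaller effect on the analysis. SAP Section 9.3 plans plots of mean hemoglobin over time and summaries of change at each post-baseline visit. SAP Appendix A makes anemia an event of special interest, found by searching reported event terms. Symptomless anemia that nobody measures is unlikely to be reported, and so would not be found by that search.

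**Working it through.** **Inputs**

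- A month is 28 days (Protocol 1.3, Definition of Terms).
- On-site visits have a window of 4 days either side; Day 1 has none (Protocol Table 1).
- On-site visits after Day 1 fall every 3 months, from Month 3 to Month 48 (Synopsis; Appendix C).
- About 500 subjects are randomized (Protocol 8.2).

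**Reading the schedule.** The Year 1 rows were counted cell by cell against the 18 column heads: Washout, Screening, Product Collection, Day 1, Months 1 to 12, Unscheduled and Premature Discontinuation. The vital-signs row served as an alignment check. Its treatment-period marks fall on Day 1, Months 3, 6, 9 and 12, Unscheduled and Premature Discontinuation, as they should.

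| Row | Day 1 | M3 | M6 | M9 | M12 | Unscheduled | Premature disc. |
|---|---|---|---|---|---|---|---|
| Full panel, with hematology | X | – | – | – | X | – | X |
| Lipids and four liver tests | – | X | X | X | – | – | – |

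The pattern repeats in Years 2 to 4: the full panel is marked only at Months 24, 36 and 48 and at Premature Discontinuation.

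**Length of the gap**

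- Day 1 to Month 12: 12 x 28 = 336 days. This matches the top duration category for the placebo-controlled period in SAP Section 6.0 (336 days or more).
- With the Month 12 window: 336 - 4 = 332 to 336 + 4 = 340 days.
- With the 30-day COVID-19 allowance for blood draws: up to about 336 + 30 = 366 days.

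**Coverage**

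- Year 1: hematology at 1 of 4 on-site visits after Day 1.
- 48 months: 48 / 3 = 16 on-site visits after Day 1, with hematology at 4.

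**If hemoglobin is added at Months 3, 6 and 9**

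- Scheduled post-baseline values in Year 1 rise from 1 to 4.
- The longest nominal gap falls to 3 x 28 = 84 days (12 weeks instead of 48). With both visits windowed it is 84 - 8 = 76 to 84 + 8 = 92 days.
- Extra assays: at most 3 x 500 = 1,500.

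**Effect on the SAP outputs.** On scheduled data, the hemoglobin plot for the placebo-controlled year has one post-baseline point. Minimum, maximum and final post-baseline hemoglobin for that year are then the same value.

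**The case against.** The strongest reply is that the schedule is deliberate and the conflict is one of wording. Safety blood of some kind is drawn at every Year 1 on-site visit, the synopsis does not mention hematology, and Appendix C is named as governing. The same pattern of a reduced interim panel and a full annual one appears in all four years, and the reduced panel tracks the drug's known lipid and liver signals. On this view, how often to check hemoglobin is a matter of preference. It is true that sites are not left with two operative instructions. But Appendix C reserves the label in the synopsis for the panel with hematology and names the interim row differently, so the synopsis needs correcting in either case.

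The second reply is that other safeguards exist. Adverse events are reviewed at monthly contacts, clinical judgment and standard of care take precedence, unscheduled visits are possible, and the discontinuation visit includes hematology. Women below 12 g/dL at entry already come under the iron rule, and for those already taking iron a new low value would not trigger it again. These points narrow the group at risk. They do not supply the missing measurement: symptom review does not detect a hemoglobin below 12 g/dL in a woman without symptoms.

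The third reply is that relevant material lies outside these documents. The separate iron instructions, and the operations manual that SAP Section 9.3 cites for laboratory tests, might call for interim hemoglobin. That cannot be settled here. If they do, the requirement should also appear in Appendix C.

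Finally, the current text already provides for subjects who have completed Month 36. A Year 1 change cannot help them, and the documents do not say whether anyone remains in Year 1. This limits the practical benefit; it does not alter the finding about the plan.

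**Conclusion.** The concern holds. A continuing subject has no scheduled hemoglobin for 336 days (332 to 340 with the visit window) during the placebo-controlled year. The synopsis implies otherwise, and the iron rule relies on a value the schedule does not provide.

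The finding is about scheduled testing only. It assumes that the label has the same meaning in the synopsis as in Appendix C, and that the separate instructions do not already require interim hemoglobin. The number of women who would become anemic in the gap cannot be derived from the documents. The Month 12 comparison between arms stands. The loss is in safety monitoring, chiefly on placebo, and in what the SAP can show about hemoglobin and anemia before Month 12. The change should be made, but the gap does not undermine the trial's main results.

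**What to change.** Add hemoglobin, or the whole hematology panel, to the Year 1 table of Appendix C at Months 3, 6 and 9, and reword the Year 1 synopsis sentence to match. Do this in both arms, since the period is blinded. In Years 2 to 4 every subject takes active drug and the need is lower, so the annual panel can stay provided the open-label synopsis sentence is reworded to say that hematology is annual. If the separate iron instructions already require interim hemoglobin, carry that requirement into Appendix C.

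Blood is already taken at Months 3, 6 and 9 for lipids, liver tests, estradiol and drug levels, so no visit or venipuncture is added. The assay cost is at most 1,500 tests. The text change is one Appendix C row and two synopsis sentences. It also needs an amendment with ethics approval at about 175 sites and a change to the central-laboratory collection. If no subject remains in Year 1, only the rewording is still useful.
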